includes the fortification of centrally produce wheat and maize flour. However, many regions in the country consume flour mostly produced by small and medium size millers. Before establishing a food fortification program that will cover these flour producers the Tanzania government wants to understand the current coverage and extension of their food fortification program in the Morogoro region because it is a microcosms of the country. The main objective of the Morogoro Region Micronutrient Household and Biomarker Study is to assess the nutritional status of anemia and other micronutrients, namely iron, vitamins 9 (folic acid) and B12, vitamin A and other indicators among women of reproductive age (15 - 49 years of age) in urban and rural areas within the Morogoro region.

2 Background and Rationale

Mandatory fortification of food products has been an effective global strategy to ensure adequate micronutrients in women of reproductive age (WRA) and reduce various micronutrient deficiencies, including that of folic acid and anemia. Maternal micronutrient deficiencies are important to address because they can lead to birth defects and other adverse birth outcomes. (Butha et al, 2008, Black et al. 2008). For example, folic acid is a water-soluble B9 vitamin needed for cell growth and development. Folate deficiency due to inadequate daily consumption of folic acid during the periconceptional period increases the risk for neural tube defects (NTDs, such as anencephaly, spina bifida, and encephalocele), and anemia (CDC 1992; IOM 1998; Bailey et al, 2015; Garret et al., 2018).

Micronutrient deficiencies continue to be a significant public health problem in Tanzania among WRA. According to the 2015-16 Tanzania Demographic and Health Survey (Table 1), a high proportion of WRA suffer from inflammation (27.8%), anemia (45%), vitamin A deficiency (42%), and iron deficiency (30%) (Tanzania MOH, 2016). The rates are slightly higher in Morogoro, in the eastern part of the country.

Micronutrient	National ¹ (%)		Morogoro ² (%)	Dar es Salaam ³ (%)
	2010	2015		
CRP (>3 mg/L)		27.8	23.5	
Anemia ^{1,2}	40.0	45.0	47.3	
Vitamin A		42.0	43.0	
Iron deficiency (sTfR>8.3µg/ml)		29.9	30.3	
Serum Folate		UNK	UNK	26.9
Red Blood Cell (RBC) folate deficiency (< 305 nmol/L)		UNK	UNK	
RBC Insufficiency (<748 nmol/L)		UNK	UNK	
Vitamin B12 Deficiency (< 148 pmol/L)		UNK	UNK	
Vitamin B12 Marginal deficiency (148 pmol/L<=B12<=221 pmol/L)		UNK	UNK	

 Table 1. Prevalence of Inflammation, Anemia and selected Micronutrients Deficiencies among women of reproductive age, Tanzania 2010, 2015

¹ Ministry of Health, Community Development, Gender, Elderly and Children 2016 ² National Bureau of Statistics (NBS) and ICF Macro. 2011. ³ Noor RA et al., 2017.

To address the ongoing micronutrient deficiencies in the Tanzanian population, the government passed food fortification legislation in 2011 that requires all industrially milled wheat and maize flour to be fortified with zinc, iron, folic acid, and other B vitamins. However, serious obstacles in the pathway of the implementation, such as decentralized milling of maize flour, have impeded the coverage of appropriately fortified food from reaching vulnerable populations in the country. Most wheat flour that is consumed in Tanzania is industrially produced but only about half of the population consumes it and most of the consumers are from urban areas. On the other hand, maize flour is consumed by 93% of the population (FACT, 2015). However, coverage of fortifiable (packaged) maize flour is a challenge because of the consumption of unpackaged flour and the use of toll mills throughout the country; the current maize flour fortification strategies exclusively target mills who produce packaged maize flour.

Maternal deficiency of folic acid has been reported to contribute to a significant proportion of birth defects in Tanzania. A study in Dar es Salaam, Tanzania found the prevalence of major external birth defects to be 28.3 per 10,000 live births and prevalence of NTDs to be 9.9 per 10,000 live births. Among stillbirths and infants who died within 5 days, NTDs were the most frequently detected birth defect (Kishimba RS, et al., 2015). The NTD prevalence reports were based on hospital information, and these reports might underestimate the true NTD prevalence. Moreover, this report probably provides a glimpse of the NTD prevalence in the country.

 - ii. To determine the methylenetetrahydrofolate reductase (MTHFR) gene mutation status of women
 - iii. To determine the consumption of key foods, specifically wheat and maize flour, among households and non-pregnant WRA
 - iv. To assess the iron, folic acid, and vitamin B12 supplementation among non-pregnant WRA
 - v. To assess the factors contributing to micronutrient deficiency among non-pregnant WRA respondents
 - vi. Assess the proportion of household with fortified wheat and/or maize flour for iron content by taking small samples of flour from half of the selected households

4 Methodology

4.1 Data Collection

Morogoro Region Micronutrient Household and Biomarker Survey

The survey will be conducted on a sample of households selected from all seven districts in the Morogoro region. Data will be collected on electronic tablets.

Criteria for inclusion/exclusion of subjects include:

- *i.* Inclusion criteria for study participants
 - a. Household residents who are present in their households at the time of the interview (or during 2 additional visits the same day)
 - b. Household has resided in current dwelling for at least 3 months
 - c. Individuals who consent to participate in the survey and prepare or purchase food for the household
 - d. At least one non-pregnant WRA (15-49 years) residing in the household
- *ii.* Exclusion criteria for study participants
 - a. Any household that does not meet inclusion criteria will be excluded.

4.2 Sample Size

The sample size was determined based on the estimated prevalence, the desire precision as well as funds available, taking into account an expected maximum non-response of 70% (including refusals) at both the household and individual levels. Table 1 provides prevalence estimates for different biomarkers in Tanzania. For those biomarkers for which we do not have information, we have assumed a prevalence of 50% (most conservative approach). The sample size required for this survey is ~1170 women. This sample size takes into account urban and rural representation with 80% power, a precision of 95%, a margin of error of 5%, a design effect of 2, and a response rate of 68% (Henderson, 1982; Lemeshow, 1985; Rosenthal et al. 2017)).

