4.4 Sampling Procedure and Sample Allocation

This is a cross-sectional household-based survey with a sample size of 1170 non-pregnant women of reproductive age. The Morogoro region encompasses seven districts, and 45 clusters will be selected from all districts (20 from urban strata and 25 from rural strata).

Data from the 2012 Tanzania Population and Housing Census for the Morogoro region (Table 2) will provide the sampling frame for this survey. Because regional differences in the distribution of rural compared with urban populations in the region, a stratified, multistage probability sample will be used for urban and rural areas. This survey will allow for independent estimates for WRA (Henderson & Sundaresan, 1982). The first stage of the sample design will be the selection of enumeration areas (EA) with probability proportional to size (PPS) design (20 urban and 25 rural areas) (Lemeshow & Robinson, 1985). The Probability Proportional to Size (PPS) design will ensure proper representation by district and population distribution. In the second stage, 26 households will be selected from each EA (totaling 1170 women). To select the households, household listing and maps of their location will be conducted in all the selected EAs prior to the initiation of survey data collection. A household listing form will be used to identify and select eligible households. A two-member team, comprising one mapper and one lister, will visit each EA to locate and mark its physical boundaries. The mapping team will do a census of all households and prepare a list of households with the name of the head and address or location of each household. During household listing, a list of household members, including the individual who prepares and/or purchases food for the household and WRA between 15 - 49years of age. In order to ensure that the household listing is current and to minimize nonresponse, the time period between household listing and the start of data collection will not exceed one month. Only one WRA participant per household will be selected.

The survey findings will be generalizable to the Morogoro region.

Table 2: Distribution of Morogoro región households, number of EAs by district and by type of residence (Census 2012).

District	Number	of Househo	olds	Number	of EAs	
	Rural	Urban	Total	Rural	Urban	Total
Kilosa	71836	30079	101915	762	358	1120
Morogoro	2328	73019	75345	24	688	712
Municipal						
Morogoro Rural	70369	3021	73390	756	30	786

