4.6 Data management and analysis

Data from the Morogoro Region Micronutrient Household and Biomarker Survey will be analyzed in SAS 9.4. Sampling weights will be applied and prevalence estimates will be calculated. Free text data will be translated into English and coded into categories before being analyzed.

Analysis and Statistical methods

The basic analysis is aimed at identifying the number of selected women of reproductive age with anemia, folate or vitamin deficiency, ferritin and retinol deficiency. Participants will be classified deficient based on each biomarker cut-off (Table 3).

Outcome Measures and Analysis

Descriptive analysis will include frequencies, mean and geometric mean values for each biomarker. In addition, for each biomarker prevalence will be determined with 95% confidence intervals. Risk factor analysis will be carried out to determine prevalence risk ratios (PRR), and 95% confidence intervals (CI) for single and combined deficiencies. Significance will be determined for contingency tables by Wald's X2 test. In addition, bivariate and stratified analyses will be performed to examine the association between independent variables and deficiency status and potential confounding and interaction effects. Independent variables that are significantly associated with deficiency status in bivariate analyses will be included in logistic regression models to determine the relative contribution of health services and access factors controlling for other factors. Independent variables will be analyzed as categorical variables. Potential multi-co-linearity among variables will be examined. Continuous outcome variables analysis will be also carried out.

Biomarker indicators

Biomarkers are biochemical, functional or clinical indices of an individual's nutrient intake, status or functional effects. They are required to support evidence-based clinical guidance for health programs and policies for nutrition and health of a population. These indices can reveal information about biological or physiological responses to dietary and behavior or pathogenic processes, as well as can be used to monitor responses to therapeutic interventions and to provide information on inter-individual differences in response to diet and nutrition.

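### Section 4.2 attaches 80% power to no comparison, and at the 5-point scale given that power is incompatible with the stated design effect and response rate at 1170 women

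*Protocol*

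**What the plan says.** Protocol section 4.2 gives the size in one sentence, "The sample size required for this survey is ~1170 women", and its basis in the next: "This sample size takes into account urban and rural representation with 80% power, a precision of 95%, a margin of error of 5", followed by "a design effect of 2, and a response rate of 68" (the 5 and the 68 are percentages). Prevalence is taken as 50% where nothing is known. The section names no null value, no contrast and no difference to detect. Its opening sentence allows for a maximum non-response of 70%, which does not agree with a 68% response rate.

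Section 4.4 fixes the design: "45 clusters will be selected from all districts (20 from urban strata and 25 from rural strata"), with 26 households in each, so 45 × 26 = 1170.

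Section 4.6 plans prevalences with 95% confidence intervals. It also plans comparisons: "Risk factor analysis will be carried out to determine prevalence risk ratios (PRR), and 95% confidence intervals (CI) for single and combined deficiencies", with Wald tests and logistic models whose variables are chosen by bivariate significance.

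**The concern.** The sentence lists power, confidence, margin, design effect and response as properties that one number has at the same time. A precision calculation has no power, and a power calculation needs an effect, which is not given. The only quantity on an effect scale is the 5% margin, and it stands beside the 80%.

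The primary objective is descriptive, so the prevalence estimates are not at risk. What is at stake is how the comparisons are read. Secondary objective v looks for factors behind deficiency, and bivariate significance decides which variables enter the models. Someone who takes 80% power from section 4.2 may read a non-significant factor, or a non-significant urban–rural gap, as evidence that no difference exists.

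**Working it through.** **Inputs.** From section 4.2: margin d = 0.05, design effect (DEFF) 2, response 0.68, prevalence p = 0.5, power 80%. From section 4.4: 20 urban and 25 rural areas, 26 households each. Assumed: two-sided 5% test, 5% read as absolute points, and variance inflated simply by the DEFF.

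**1. The plan's figure as a precision calculation**
- 1.96² × 0.25 / 0.05² = 384.1
- 384.1 × 2 / 0.68 = 1129.8
- 1129.8 / 45 = 25.1 households per area, rounded up to 26; 26 × 45 = 1170

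This uses every stated input except the power.

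**2. The plan's figure as a power calculation for 5 points against a fixed value**
- (1.96 + 0.84)² × 0.25 / 0.05² = 784.9 (unrounded normal quantiles)
- Response but no DEFF: 784.9 / 0.68 = 1154; 1154 / 45 = 25.6, again rounded up to 26 and 1170
- Response and DEFF: 784.9 × 2 / 0.68 = 2308

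So 1170 can carry the DEFF of 2 or 80% power at 5 points, but not both.

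**3. Power at 1170 with all stated inputs**
- Respondents: 1170 × 0.68 = 795.6; effective n = 795.6 / 2 = 397.8
- SE = 0.5 / √397.8 = 0.0251
- Power for 5 points against a fixed value: Φ(0.05 / 0.0251 − 1.96) = 51.4%

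Changing one assumption at a time:

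| Change | Power |
|---|---|
| Exact binomial | about 48% |
| 70% response | 52.5% |
| Prevalence 30.3% (iron deficiency, Morogoro, Table 1) | about 58% |
| One-sided test | 63.7% |
| Prevalence 23.5% (CRP, Morogoro, Table 1) | about 65% |
| 100% response | 67.7% |
| DEFF 1 | 80.5% |

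Of these, only dropping the DEFF reaches 80%.

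**4. Urban versus rural**
- Effective n: 20 × 26 × 0.68 / 2 = 176.8 urban; 25 × 26 × 0.68 / 2 = 221 rural
- SE of the difference: 0.5 × √(1/176.8 + 1/221) = 0.0505
- Power for 5 points: about 17%
- Difference with 80% power: 2.80 × 0.0505 = 0.141, about 14 points

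**5. Precision that 1170 delivers**
- Region: 1.96 × 0.5 / √397.8 = 4.9 points
- Urban: 1.96 × 0.5 / √176.8 = 7.4 points
- Rural: 1.96 × 0.5 / √221 = 6.6 points

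**6. Dependence on the response rate.** If 70% non-response were meant, the effective n is 1170 × 0.30 / 2 = 175.5. The regional margin becomes 7.4 points and the power in step 3 about 26%.

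**The case against.** The strongest reply is that the protocol never says the 80% is for a 5-point difference; it calls 5% a margin of error. Power at a difference equal to the confidence-interval half-width is about 50% by construction, so the 51% largely restates that the number suits a precision target. This stands. A reader might infer that section 4.2 promises 80% power for 5 points and falls short of it; the text sets no such target. What it does is give a power with no effect, next to inputs that exclude that power at the only scale shown.

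A reader might also infer that 1170 can come only from the precision formula. It cannot be said that firmly: 1154 is nearer to 1170 than 1130 is, and it too rounds to 26 per area. The field and laboratory protocol (Appendix 8.3, Introduction) gives 55 clusters of 21 households, which is 1155, and 790 participants, a ratio of 68.4%. Those figures lie close to 1154 and 785. They conflict with section 4.4 and may be left-over text, and 790 is also near the 768 (384.1 × 2) of the precision route. They settle nothing, but they leave open that a power formula was used and the DEFF omitted.

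Third, the harm is limited. Section 4.2 says precision and funds drove the number, intervals will be reported, and no urban–rural test is specified. That keeps this a matter of wording, but it does not make the stated power right.

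**Conclusion.** The point holds in this form: the 80% is undefined, and at the 5-point scale it cannot hold together with a DEFF of 2, 68% response and 1170 women. With all stated inputs, power for 5 points is about 51% against a fixed value and about 17% between urban and rural women; 80% power at 5 points against a fixed value would need about 2308 women.

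This rests on p = 0.5, a two-sided 5% test, absolute points, 68% response, and a DEFF of 2 that covers both clustering and weighting.

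One further reading should be resisted. The difference with 80% power against a fixed value is 2.80 × 0.0251, about 7 points, and a reader might take this as the limit for the section 4.6 associations. Section 4.6 plans no test against a fixed value. For two equal groups (198.9 effective women each at DEFF 2) the difference is 2.80 × 0.5 × √(2/198.9), about 14 points; at DEFF 1 (397.8 each) it is about 10. Uneven splits need more, and factors that vary within clusters may have a smaller DEFF, so no single figure serves.

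**What to change.** 1. First reconcile the 70% non-response with the 68% response rate in section 4.2, since every figure here depends on it.
2. Say which calculation produced 1170.
3. Delete the 80% power. State instead what 1170 delivers: 95% confidence and about ±4.9 points for the region, ±7.4 urban and ±6.6 rural, at 50% prevalence, DEFF 2 and 68% response.
4. If a power figure is kept, tie it to a named comparison and restate it at 1170, for example 80% power for a difference of about 14 points between urban and rural women. Do not offer 7 points as a limit for section 4.6; the detectable difference there depends on the group split and the design effect.

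The cost is one rewritten paragraph and a less favourable power statement. The correction calls for no more women, clusters or laboratory work.

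### Section 4.2 gives response assumptions that do not agree, and its 1170 is a number selected that supports a 5-point margin only for the region as a whole

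*Protocol*

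**What the plan says.** Section 4.2 says the size of about 1170 women rests on estimated prevalence, desired precision and available funds, and allows for an "expected maximum non-response of 70% (including refusals) at both the household and individual levels". For biomarkers without prior data, "we have assumed a prevalence of 50% (most conservative approach"). It then lists the inputs: "This sample size takes into account urban and rural representation with 80% power, a precision of 95%, a margin of error of 5" per cent, together with "a design effect of 2, and a response rate of 68" per cent.

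Section 4.4 repeats the number as the size of the survey ("This is a cross-sectional household-based survey with a sample size of 1170 non-pregnant women of reproductive age") and fixes the allocation: "45 clusters will be selected from all districts (20 from urban strata and 25 from rural strata"), with 26 households per enumeration area (EA) and one woman per household. Table 2 puts 30% of the region's households in urban and 70% in rural areas.

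**The concern.** Four things in one short section do not fit together.

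- The two response figures do not describe one plan. A non-response of 70% leaves 30% responding; the other figure is 68% responding.
- The number 1170 is called the sample size in women, but a size already inflated for non-response is a number to select, not a number to analyse.
- The 5% margin stands in a sentence that invokes both urban and rural areas, without saying whether it applies to the region or to each stratum.
- Power is quoted with no comparison and no difference to detect.

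At stake is what a reader expects from the results: how many women will have biomarker data, and how wide the intervals will be for the region and for each stratum. The choice of women, the weighting and the analysis are not affected.

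**Working it through.** **Inputs.** From section 4.2: prevalence 50%, margin 5 points, 95% confidence (z = 1.96), design effect 2, response 68%. From section 4.4: 20 urban and 25 rural EAs, 26 households each, so 520 + 650 = 1170 selected. From Table 2: household shares 30% urban, 70% rural.

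**1. Reproducing 1170.** For one proportion, n = z² p(1−p)/d² × design effect / response.

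- 1.96² × 0.25 / 0.05² = 384.1
- 384.1 × 2 = 768.3 women with results
- 768.3 / 0.68 = 1130 women selected
- 1130 / 45 = 25.1 per EA, rounded up to 26; 26 × 45 = 1170

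The figure is therefore reproduced as one regional estimate. Nothing in it is doubled for two strata; ±5 points in each stratum would need 2 × 1130 = 2260 selected.

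**2. The other response figure.** With 70% non-response, 768.3 / 0.30 = 2561 selected. If the 70% was meant as response, 768.3 / 0.70 = 1098, or 24.4 per EA, which rounds up to 25 and gives 1125. Neither gives 1170.

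**3. Margins from the 1170 selected.** Half-width = 1.96 × √(2 × 0.25 / n), where n is the number with results and the design effect of 2 is applied in each stratum.

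| Response assumed | Region: n, margin | Urban: n, margin | Rural: n, margin |
|---|---|---|---|
| 68% overall | 796, ±4.9 | 354, ±7.4 | 442, ±6.6 |
| 68% at each of two levels (0.68² = 46%) | 541, ±6.0 | 240, ±8.9 | 301, ±8.0 |
| 30% (70% non-response, counted once) | 351, ±7.4 | 156, ±11.1 | 195, ±9.9 |
| 100% | 1170, ±4.1 | 520, ±6.1 | 650, ±5.4 |

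With 68% overall response and the Morogoro prevalences in Table 1 for anemia, vitamin A and iron deficiency (47.3%, 43.0%, 30.3%), the margins are ±6.8 to ±7.4 urban and ±6.1 to ±6.6 rural.

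**4. Unequal weighting.** Urban areas supply 20/45 = 44% of the sample but 30% of households. The variance factor is 0.3²/(20/45) + 0.7²/(25/45) = 0.2025 + 0.8820 = 1.0845. If the design effect of 2 does not already include it, the regional margin is 4.91 × √1.0845 = 5.1 points.

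**5. Power.** It does not enter the formula in step 1. Taken as an urban–rural comparison at 68% response, the effective sizes are 354/2 = 176.8 and 442/2 = 221 (from the unrounded 353.6 and 442). The difference detectable with 80% power is (1.96 + 0.842) × √(0.25/176.8 + 0.25/221) = 14.1 points.

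**The case against.** The strongest reply is that the protocol makes no promise about the strata. A reader might infer from section 4.2 that ±5 points was guaranteed separately for urban and rural women, and that the survey misses a stated target. The text does not say so. Representation can mean simply that both strata are sampled, which the 20/25 allocation does. Section 4.4 describes findings that apply to the Morogoro region and weights normalized at regional level. That stands: the margin's domain is unstated, not misstated. It still needs stating, because the opening summary sets the aim in urban and rural areas and the sizing sentence names both.

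A reader might also infer that the survey is underpowered for an urban–rural contrast on which its purpose depends. No listed objective is such a contrast; rural access to fortified flour is background.

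On response, 70% is called a maximum and 68% may be the planning value, so the two are not a strict logical contradiction. But section 4.2 says the size allows for both, and a size that allowed for 70% loss would be 2561. A slip is likely, so a reader should not conclude that only 351 women are expected. Turning the 70% into a response rate does not fully settle it either: that would make the maximum non-response 30%, while 68% response implies 32%.

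Finally, section 4.2 does mention the response rate, and section 4.4 ties 1170 to households selected, so a careful reader could work out the analysed number. The field and laboratory protocol (section 8.3) even gives 790 participants from 55 × 21 = 1155 households, a ratio of 68.4%. That supports the selected-versus-analysed reading, although its cluster plan differs from the 45 × 26 of section 4.4 and must itself be reconciled.

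**Conclusion.** The point holds as an inconsistency in how the sample-size basis is stated, and it should be fixed. It is not an error in the 1170, which follows from the section's own inputs for one regional proportion.

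- Only a response near 68% fits 1170. The 70% non-response figure does not.
- 1170 is the number selected; about 796 women are expected with results.
- The 5-point margin is supported for the region only: ±4.9, or about ±5.1 if weighting is extra. The strata have about ±7.4 (urban) and ±6.6 (rural). Even full response would not bring either stratum to ±5 at 50% prevalence.
- The 80% power has no role in the calculation.

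The stratum figures assume 50% prevalence, a design effect of 2 within each stratum, and 68% as the combined household-and-individual response. The protocol settles neither of the last two. If 68% applies at each level, the margins become about ±6.0, ±8.9 and ±8.0, and the regional target is missed too.

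**What to change.** Reword section 4.2, and the matching sentence in section 4.4, with no change to enrolment, clusters or allocation:

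- Keep one response assumption, and say whether 68% is the combined household-and-individual rate or applies at each level. Correct or delete the 70% non-response figure.
- State 1170 women selected and the expected number analysed (about 796 if 68% is the combined rate).
- State that the 5-point margin applies to the region, and give the expected urban and rural half-widths with the prevalence, design effect and response they assume. Say whether the design effect of 2 includes unequal weighting.
- Call the 95% figure a confidence level, not a precision.
- Delete the 80% power, or tie it to a stated difference (about 14 points urban versus rural on these inputs).

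The cost is protocol wording only. The stated precision for the strata will look less favourable than a reader may now assume.
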